7.3 Adverse Events and Serious Adverse Events

An adverse event (AE) is any untoward medical occurrence in a subject during participation in the clinical study or with use of the experimental agent being studied. An adverse finding can include a sign, symptom, abnormal assessment (laboratory test value, vital signs, electrocardiogram finding, etc.), or any combination of these regardless of relationship to participation in the study.

A serious adverse event (SAE) is one that meets one or more of the following criteria:

- Results in death
- Is life-threatening (places the subject at immediate risk of death from the event as it occurred)
- Results in inpatient hospitalization or prolongation of existing hospitalization
- Results in a persistent or significant disability or incapacity
- Results in a congenital anomaly or birth defect

An important medical event that may not result in death, be life threatening, or require hospitalization may be considered an SAE when, based upon appropriate medical judgment, the event may jeopardize the subject and may require medical or surgical intervention to prevent one of the outcomes listed in this definition. A suicide attempt will be considered an SAE.

Unanticipated problems are defined as any incidence, experience, or outcome that is:

- Unexpected (in terms of nature, severity, or frequency) given the information provided in research-related documents and the characteristics of the subject population being studied;
- Related or possibly related to participation in the research; and
- Suggests that the research places subjects or others at a greater risk of harm than was previously known or recognized.

Adverse Events, Unanticipated Problems and Serious Adverse Events will be recorded by study staff throughout the study occurring any time after informed consent is obtained until 7 (for non-serious AEs) or 30 days (for SAEs) after the last day of study participation. These will be recorded in an Excel document and kept on file in an electronic secure UMN Box folder for the study. There will be no identifying information recorded in this document and subjects will be identified by subject ID number (GRID number). In addition to whether AE was UP or SAE, details of event, and date of occurrence, we will also label organ system where it occurred (general, psychiatric, nervous system, etc.), severity, expectedness, relationship to study, if it was reported and date of reporting if so, day of trial it occurred (i.e. 1-32), if resolution/stabilization occurred and date of resolution/stabilization. All adverse events will be reviewed with the assigned Independent Clinical Monitor to assist in characterizing the adverse event (e.g. relatedness to study drug, determining if it should be classified as an Unexpected Problem), whether the new information warrants a change to the protocol or consent form (e.g. description of risks) and whether a dose change or participant withdrawal is indicated.

At each study visit (Days 1, 14, and 28 - 32) study staff will inquire about the occurrence of AE/SAEs since the last visit. If AE is ongoing and resolution of AE

has not occurred at time of reporting by subject, study staff will assess resolution/stabilization 1 week later via phone contact. Study staff will cease to assess previous AE of a participant 2 weeks after last day of study participation by that participant.

Safety review by Independent Monitoring Committee will occur if resolution of AE has not occurred 2 weeks after discontinuing study drug (due to study completion or dropout) and AE is considered to be related to study intervention (possibly, probably or definitely) by study PI.

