Participants will return to the CMRR for a 3-8 hour visit ~4-weeks after beginning study drug, on Day 28 - 32 and present their remaining medications for capsule count to assess drug compliance. This visit will entail a repeat of the baseline neuroimaging procedure and multiple blood collections for PK analysis. The participant will be asked if they would prefer placement of IV catheter versus a series of needle sticks every time a blood sample is collected. We will collect an initial blood sample to measure trough NAC and CYS levels, as well as oxidative stress measurements detailed below. Then, participants will take their final oral dose. We will collect additional blood samples (2-5) starting at 15 minutes and ending at ~120-300 minutes following the final oral dose to measure NAC and CYS levels (abbreviated COVID-19 protocol: just 2 post-NAC dose blood draws, one right before and one right after the MRI scan). Neuroimaging will begin ~15 minutes after the final dose and will last ~60-90 minutes. Following this MRI scan, participants will be interviewed to ascertain medication side effects using a checklist. Although this study is not designed to examine clinical effects, to allow for exploratory analyses examining links between concurrent symptoms and biology, we will ask participants to complete the ABUSI, an abbreviated form of the SITBI (modified to query the NSSI thoughts, urges and behaviors since the prior clinical assessment), the ISAS-SLV to assess NSSI episodes, BDI-II, PHQ-9 and BSSI to assess depression symptoms and current suicidal thoughts and behaviors, the DSHQ-M to assess mood in relationship to NSSI episodes, and the one-question Cash Choice Task as a delay discounting measure (Wulfert et al., 2002) . The PHQ-9, ISAS-SLV, ABUSI, DTS, Cash Choice Task, Side Effect Checklist, and Ongoing Medication Uses and Changes: Subsequent Visits will be available online via REDCap. Paper versions will be available if necessary (REDCap down, computer unavailable, etc.) Participants who are unable to complete all online self-report questionnaires in-person due to time constraints will be emailed an access code for each questionnaire and a link to the REDCap website. Upon opening the website link, they will be prompted to enter their access code in order to fill out questionnaires. Upon administration of the final dose of study drug, participants will be instructed to inform study staff of any potential adverse effects that occur after leaving the research facility. In addition, 24-72 hours after the final dose of NAC, participants will receive a phone call from study staff to assess any potential adverse effects after the final dose of study drug and address any lingering questions/concerns about study participation and/or referral suggestions for future

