7.5 Follow-up for Adverse Events

If AE is still present at the time it is reported, it will be re-assessed one week later either in person, via online survey or via phone. If the AE is still present 2 weeks after last day of study participation, it will be considered stable, and we will not continue assessments. Safety review by Independent Monitoring Committee will occur if resolution of AE has not occurred 2 weeks after discontinuing study drug (due to study completion or dropout) and AE is considered to be related to study intervention (possibly, probably or definitely) by study PI and the Independent Clinical Monitor.

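### After the 24-72 hour call, SAE capture to day 30 rests on spontaneous report, and the two-week stop in AE assessment has no SAE exception and conflicts with the one-week re-assessment rule

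*Combined protocol and SAP*

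**What the plan says.** **Recording window.** Section 7.3 records adverse events from consent "until 7 (for non-serious AEs) or 30 days (for SAEs) after the last day of study participation". The same section classes a suicide attempt as an SAE.

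**Planned enquiry.** Section 7.3 states: "At each study visit (Days 1, 14, and 28 - 32) study staff will inquire about the occurrence of AE/SAEs since the last visit". Section 6.2.5 adds that "24-72 hours after the final dose of NAC, participants will receive a phone call from study staff to assess any potential adverse effects". That call is the last column of the schedule in 6.1, and nothing is scheduled for all participants after it.

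**Follow-up of open events.** Section 7.5: "If AE is still present at the time it is reported, it will be re-assessed one week later". Section 7.3 has the same one-week rule, by telephone.

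**End of assessment.** Section 7.3: "Study staff will cease to assess previous AE of a participant 2 weeks after last day of study participation". Section 7.5 says of an AE still present at that point that "it will be considered stable, and we will not continue assessments". Neither sentence excepts SAEs.

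**The log.** Section 7.3 asks for the trial day of the event, described as running from 1 to 32, and for whether and when the event resolved or stabilised.

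**The concern.** The windows were not fitted to each other. The SAE window is the longest, but both the last planned contact and the end of assessment fall well inside it. Three consequences follow.

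1. Late SAEs reach the team only if someone volunteers them. A participant who has been hospitalised, is incapacitated or has died is poorly placed to do so.
2. For an SAE reported late, one rule calls for a re-assessment and another says that assessment has ended. Staff cannot follow both.
3. An event that is unchanged or worsening at two weeks can be entered as stabilised on a date set by the calendar.

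Section 7 says that this population is at increased risk of suicide attempts. The suspension thresholds in 9.4 are proportions of participants who have received study intervention, with no stated end of observation, so a missed event counts as no event. The adverse event rates to be compared between groups in 9.6 would be incomplete in the same way for any post-treatment period they include. A low post-treatment SAE count could not be read as absence of harm after study drug ends.

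**Working it through.** No power, alpha or event rate bears on this point, and the plan gives no figure to reproduce. The check is a count of days on the stated windows.

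**Inputs**
- SAE window 30 days, non-serious AE window 7 days, both after the last day of participation (7.3).
- Final call 1 to 3 days after the final dose (6.2.5).
- Re-assessment 7 days after report if the event is still present (7.3, 7.5).
- Assessment stops 14 days after the last day of participation (7.3, 7.5).
- Final visit on Day 28-32, or up to Day 35 if rescheduled (6.2.5).
- The last day of participation is not defined. It is taken first as Visit 4, with the final dose given there, and then as the call itself.

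**Step 1: days with no planned enquiry (participant without an open AE)**
- Last day = Visit 4: 30 − 3 = 27 to 30 − 1 = 29 of 30 days, that is 90% to 97%.
- Last day = the call: 30 of 30 days.
- Non-serious AEs, last day = Visit 4: 7 − 3 = 4 to 7 − 1 = 6 of 7 days.

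**Step 2: one-week rule against two-week stop**
- An ongoing event reported on day d is due for re-assessment on day d + 7.
- This is no later than the stop if d + 7 ≤ 14, that is d ≤ 7.
- Non-serious AEs reported within their 7-day window always satisfy this, so the two rules agree for them.
- SAEs reported on days 8 to 30 do not: 30 − 7 = 23 of 30 days (77%) in which the two rules give opposite instructions.

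**Step 3: SAE days after the stop**
- 30 − 14 = 16 days (days 15 to 30), or 53% of the window. This is time inside the recording window but past the stated end of assessment. It is not the share of SAEs that go without follow-up, because the one-week rule may still be applied to them.

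**Step 4: the log field**
- The SAE window can reach trial day 32 + 30 = 62, or 35 + 30 = 65 after a rescheduled visit. The field is described as 1 to 32.

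**Step 5: the stability rule**
- Section 7.5 makes an event stable because two weeks have passed, whatever its course. Section 7.3 then has a field for stabilisation and its date. Read together, they allow an unresolved SAE to be closed with a status that no assessment supports.

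**The case against.** **Capture after the call is passive, not absent.** Participants are told to report effects that arise after they leave (6.2.5), the team follows up those who raise health concerns unprompted (7.2), and the Independent Clinical Monitor reviews all AEs (7.2, 7.3). Known SAEs carry reporting duties, including 24-hour notice to the ombudsman of a suicide attempt (7.4). This stands, and a reader who infers that late SAEs are neither sought nor followed goes further than the documents. It does not close the gap. The instruction has no end date and does not name SAEs, hospitalisation or suicide attempt, and the reporting duties begin only once the team knows of the event.

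**A recording window may be longer than the last contact.** True: 7.3 promises to record to day 30, not to ask at day 30. On this part the defect is one of design and not a contradiction. The contradiction lies between the two-week stop and the one-week rule.

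**The stop may concern only events already open.** Sections 7.3 and 7.5 speak of a previous AE and of one still present, so an SAE with onset on days 15-30 may fall outside the stop and still be re-assessed. That reading is possible. It is why the 53% in Step 3 cannot be stated as time without follow-up. The text does not settle which reading applies.

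**The Independent Monitoring Committee reviews unresolved related AEs.** A reader might infer that assessment always stops just as that review begins. The clocks differ: the review runs from stopping study drug, and the stop runs from the end of participation. As an illustration, drug stopped on day 7 with a final visit on day 28 gives a review trigger at 7 + 14 = day 21 and a stop at 28 + 14 = day 42. The two roughly coincide only for those who take study drug until Visit 4, and under 9.4 the committee may ask for further investigation.

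**Impact is limited.** Shares of days are not shares of events, and no event rate is given. The tolerability checklist ends at Visit 4 (9.5.2), the primary GSH outcome is untouched, and nothing shows that passive capture would differ by arm. Section 7 supports increased risk of suicide attempt; a reader might take it as the main risk, but the documents do not rank it so. All of this stands.

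**Conclusion.** The concern holds in a limited form. SAEs can be recorded to day 30, but after the 24-72 hour call no contact is scheduled for a participant without an open AE. Capture over about the last 27 of 30 days (27 to 30, depending on what the last day of participation means) therefore rests on spontaneous report. The two-week stop has no SAE exception and is not reconciled with the 30-day window or the one-week rule, so the instructions for SAEs reported after about day 7 conflict. The conflict in Step 2 assumes that the stop applies to every AE, as its wording allows, and that the event is still present when reported. Calling open events stable by the calendar needs no such assumption: followed as written, it puts an unobserved outcome in the log. The effect is on the completeness and meaning of post-treatment safety data, not on the primary analysis. It should be corrected.

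**What to change.** Amend 7.3 and 7.5, with matching changes in 6.1 and 6.2.5:

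1. State that the two-week stop does not apply to SAEs or to unresolved AEs judged related, and reconcile it with the one-week re-assessment rule and the 30-day window.
2. Replace the rule that open events are considered stable with a status of *ongoing at last assessment*. Enter stabilisation only when an assessment shows it.
3. Define the last day of study participation, including for participants who withdraw or stop study drug early (4.3 allows for up to 20% attrition).
4. Extend the trial-day field to cover the whole SAE window, at least to day 65.
5. Add one short telephone or REDCap enquiry at the end of the 30-day window, asking about AEs, hospitalisation and suicide attempt.

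The cost is a small protocol amendment, one brief extra contact for each of up to 46 enrolled participants using existing staff and systems, slightly longer involvement for each, and a few follow-up calls for open events. Sample size and the primary analysis do not change.

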7.4 Reporting Procedures

The Study PI, the Independent Clinical Monitor and the Independent Monitoring Committee will be responsible for determining whether an SAE is expected or unexpected. An adverse event will be considered unexpected if the nature, severity, or frequency of the event is not consistent with the risk information previously described for the intervention.

Incidents or events that meet the OHRP criteria for unanticipated problems require the creation and completion of an unanticipated problem report form. OHRP recommends that investigators include the following information when reporting an adverse event, or any other incident, experience, or outcome as an unanticipated problem to the IRB:

- Appropriate identifying information for the research protocol, such as the title, investigator's name, and the IRB project number;
- A detailed description of the adverse event, incident, experience, or outcome;
- An explanation of the basis for determining that the adverse event, incident, experience, or outcome represents an unanticipated problem;
- A description of any changes to the protocol or other corrective actions that have been taken or are proposed in response to the unanticipated problem.

To satisfy the requirement for prompt reporting, unanticipated problems will be reported using the following timeline:

- Unanticipated problems that are serious adverse events will be reported to the Independent Monitoring Committee, and NCCIH within 7 days of the investigator becoming aware of the event.
- Any other unanticipated problem will be reported to the Independent Monitoring Committee, and NCCIH within 14 days of the investigator becoming aware of the problem.

All unanticipated problems should be reported to appropriate institutional officials (as required by an institution's written reporting procedures), the supporting agency head (or designee), and OHRP within one month of the IRB's receipt of the report of the problem from the investigator.

The following will be reported to Advarra IRB, the external IRB overseeing this

research study, within 10 days:

- Unanticipated problem that adversely affects the risk/benefit ratio of the study, or rights, safety, or welfare of the participants or others, or integrity of the study. (Advarra IRB form: Safety Information and Unanticipated Problem Report)
- An adverse event that is serious, unanticipated, and [study] related. (Advarra IRB form: Safety Information and Unanticipated Problem Report)
- Any change from Board-approved protocol that adversely affects the risk/benefit ratio of the study, or rights, safety, or welfare of the participants or others, or integrity of the study. (Advarra IRB form: Safety Information and Unanticipated Problem Report)
- Any prospective request for an intentional deviation from the IRB approved protocol except when necessary to eliminate an apparent immediate hazard to a participant. (Advarra IRB forms: Copy of Sponsor approval and Prospective Waiver/ Exception Request Form)
- A complaint associated with the study regarding an alleged breach of the rights, safety, or welfare of the participants or others, or integrity of the study. (Advarra IRB form: Safety Information and Unanticipated Problem Report)
- Any adverse finding issued to, or enforcement action taken against, the PI. (Advarra IRB forms: Copy of the adverse audit results, enforcement action, etc. and Safety Information and Unanticipated Problem Report)
- Any significant problems, violations, research-related accidents and illnesses must be reported. Spills or accidents in BL2 laboratories resulting in an overt exposure must be immediately reported. (Advarra IRB form: Safety Information and Unanticipated Problem Report)

Investigators in the Department of Psychiatry conducting clinical drug trials are required to notify The Office of Ombudsman for Mental Health and Developmental Disabilities (OMHDD) within 24 hours of a U of M research participant's death or serious injury. This includes suicide attempt. The Ombudsman Reporting Transmittal Form is used by HRPP and the University of Minnesota Principal Investigator to report to OMHDD pursuant to Minnesota Statute 245.92 and 245.94. Reports of death or serious injury of locally enrolled study participants in psychiatry clinical drug trials must use the Transmittal Form as the cover page to the applicable report form available on the OMHDD website.

Reporting to Advarra IRB, the University of Minnesota IRB, the OMHDD, the NCCIH and the Independent Monitoring Committee will be performed by the Research Coordinator ([name]), Regulatory Specialist ([name]) or the Principal Investigator ([name]).

SAEs that are unanticipated, serious, and possibly related to the study intervention will be reported to the Independent Monitoring Committee, IRB, FDA, and NCCIH in accordance with requirements. For the IND:

- 7-day IND Safety Report (unexpected fatal or life-threatening AEs related to the intervention); a copy of the report sent to the FDA will be submitted to the NCCIH Program Officer and Independent Monitoring Committee within 24 hours of FDA notification.
- 15-day IND Safety Report (any other serious and unexpected AE related to the intervention); a copy of the report submitted to the FDA will be submitted to the NCCIH Program Officer and Independent Monitoring Committee within 24 hours of FDA notification.
- All other AEs documented during the course of the trial will be reported to NCCIH on an annual basis by way of inclusion in the annual report and in the annual AE summary which will be provided to NCCIH and to the Independent Monitoring Committee. The Independent Monitoring Committee Report will state that all AEs have been reviewed.

Pregnancy is an MRI contraindication and is a part of exclusion criteria. If a potential subject is pregnant, they will not pass screening as a result. If a subject becomes pregnant while enrolled in the study, they will then no longer meet criteria, be ineligible and be removed from the study. Since we conduct a pregnancy test prior to MRI scanning, this will be picked up before MRI scanning. This will be recorded in our enrollment log if occurs. Since there are no known risks associated with NAC and pregnancy, study staff will not report this immediately, but will be reported as part of the enrollment log when reporting to Advarra IRB continuing review, as well as any other reporting that includes the enrollment log (Independent Monitoring Committee, FDA, NCCIH).

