Biological Assessments: Following the informed consent, baseline clinical assessment and (if eligible) randomization, participants will be invited to the CMRR for a 2-3 hour visit. During the global COVID pandemic, for all in-person visits, upon arrival, participants will complete COVID screen, follow pandemic related safety precautions including use of face mask and social distancing as outlined in the approved sunrise plan submitted by PI [name]. They will then complete a blood draw, a urine toxicology screen, pregnancy test and an MRI safety screen, followed by neuroimaging procedures as described below. For the urine tests, the participant will provide a urine sample, and the research staff will apply the urine pregnancy test strip and the urine toxicology test strip according to the package instructions. Research staff will record the results in the CRF and discard the urine sample and the test strips according to standard CMRR procedures. If urine pregnancy test is positive, staff will not complete the MRI scan on the participant. The participant will also no longer meet criteria for the study, and will be removed from the study. If the toxicology screen is positive, results will be noted on the MRI CRF form and the participant will continue on with the MRI scan. Participants that do not pass the MRI safety screen will not receive MRI scan and will be allowed to remain in the study. Parents of participants, even those under 18 years of age, will not be informed of pregnancy or urine toxicology test results. The research team will utilize the CMRR Center's Subject Information Form and adhere to the SOP during enrollment of all research participants in this protocol. The CMRR Center's Subject Information Form and SOP are IRB approved under the CMRR Center Grant (HSC# 1406M51205) and information regarding these procedures is publicly available on the CMRR website (CMRR Policies / Procedures).

Randomization

Randomization and Double-Blind: Participants who meet criteria for entry into the study (based on the online screen and the clinical interview) and consent to participate will be randomized to active NAC high dose versus active NAC low dose versus PBO (1:1:1). We will implement an adaptive randomization procedure called minimization. The purpose of the procedure is to ensure that the 3 treatment groups

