8. INTERVENTION DISCONTINUATION

The intervention will be discontinued in the following circumstances:

- If the participant is unable to tolerate the study medication due to side effects or allergic reaction, even after decreasing the dose, as determined by a conversation between the PI (or delegate) and the participant.
- If the participant elects to no longer take the study medication.
- If the participant becomes actively suicidal with intent and plan, and cannot agree to a safety plan engaged by study team (see Supplement IV).
- If the participant or parent of minor participant withdraws consent.
- If the participant becomes pregnant.
- If the IMC or the Medical Monitor recommend participant withdrawal due to safety concerns.

Discontinuing the intervention will also be considered in the following circumstances:

- If a participant engages in NSSI with significant tissue damage that requires urgent/emergency medical care, study staff will assess safety of participant and engage participant (and parents of minors) in a safety conversation to discuss how to increase safety in the home, whether hospitalization is needed, and whether continuing in the study is appropriate (See Supplement IV). If it is deemed safe by study staff with respective input from NCCIH, FDA, Advarra IRB and/or IMC when necessary and participant (and parents of minors) desire to continue, remaining study visits will be completed.
- If a participant fails to adhere to protocol requirements, study staff will assess safety of participant with respect to protocol deviation(s) and engage participants (and parents of minors) in conversation to discuss their safety and if continuing in the study is appropriate. If it is deemed safe by study staff with respective input from NCCIH, FDA, Advarra IRB and/or IMC when necessary and participant (and parents of minors) desire to continue, remaining study visits will be completed.

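### Birth defect is a listed SAE, but no birth after study-drug exposure falls inside the SAE recording window and no pregnancy outcome is actively sought

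*Combined protocol and SAP*

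**What the plan says.** All of this is in the combined protocol and SAP.

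- **Definition.** The SAE criteria in Section 7.3 include "Results in a congenital anomaly or birth defect".
- **Recording window.** Section 7.3 has events recorded from consent "until 7 (for non-serious AEs) or 30 days (for SAEs) after the last day of study participation".
- **Follow-up of known events.** Section 7.3 adds: "Study staff will cease to assess previous AE of a participant 2 weeks after last day of study participation". Section 7.5 sets the same two-week limit.
- **Pregnancy during the study.** Section 7.4 says of such participants that "they will then no longer meet criteria, be ineligible and be removed from the study". Section 6.2.2 says the same of a positive urine test before a scan: "The participant will also no longer meet criteria for the study, and will be removed from the study".
- **Reporting of the pregnancy.** Section 7.4 says "study staff will not report this immediately, but will be reported as part of the enrollment log". The sentence goes on to send that log to the IRB at continuing review and into any other report that contains it, naming the monitoring committee, FDA and NCCIH. The reason given is that no risk of NAC in pregnancy is known.
- **Discontinuation.** Section 8 lists "If the participant becomes pregnant" among the reasons to stop the intervention. It then leaves later data collection, for all the listed circumstances, to safety, the participant's interest and adherence.
- **Contacts and tests.** Pregnancy is tested at Visits 2 and 4 only (Section 6.1). The last planned contact is a call 24 to 72 hours after the final dose (Section 6.2.5).

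**The concern.** The protocol names a class of serious event that becomes apparent mostly at birth, then sets recording rules that end within weeks of a pregnancy being found. The sample consists wholly of young women. Contraception is required (Section 4.2), but the two tests are about four weeks apart, so an early pregnancy could be exposed for most of the course before it is detected.

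What is at stake is safety ascertainment. Section 7.4 treats an event as unexpected when it does not fit the risk information already described. Because the protocol describes no pregnancy risk, a birth defect would be serious and unexpected and, if judged related, would call for a 15-day IND report. The plan creates that duty but gives staff no planned route to learn of the event. The statement that no risk is known explains why a pregnancy is not reported at once. It does not explain why its outcome is not sought.

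**Working it through.** The plan gives no derived figure to reproduce; the 30 days is a rule. The check is whether any birth after study-drug exposure can fall inside it.

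**Inputs from the protocol**
- First dose: Day 1.
- Final visit: Day 28 to 32, with supply extendable to Day 35 (Section 6.2.5).
- Final call: up to 72 hours after the final dose, so Day 38 at the latest.
- SAE recording: 30 days after last participation (Section 7.3).
- Enrolment: up to 46 (Section 4.3).

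**Assumptions, not in the documents**
- Conception to term: 266 days.
- Earliest birth considered: 22 weeks' gestation, 140 days after conception.
- Earliest conception compatible with a negative Day 1 test: 0 to 14 days before Day 1.
- Pregnancy rate: 0.2 to 1% per month.

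**Formulas**
- Window end = last day of participation + 30.
- Days since conception at window end = window end − 1 + days conceived before Day 1.
- Shortfall = 140 or 266 minus that number.

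| Last day of participation | Recording ends | Days since conception | Short of 22 weeks | Short of term |
|---|---|---|---|---|
| Day 28 | Day 58 | 57–71 | 69–83 days | 195–209 days |
| Day 32 | Day 62 | 61–75 | 65–79 days | 191–205 days |
| Day 35 | Day 65 | 64–78 | 62–76 days | 188–202 days |
| Day 38 (call counted) | Day 68 | 67–81 | 59–73 days | 185–199 days |

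These rows are the most favourable to the plan, because later conception widens the gap. Conception on Day 35 puts term at Day 35 + 266 = Day 301, which is 301 − 65 = 236 days after a Day 65 close.

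The result is not sensitive to the conception assumption. For a birth at 22 weeks to fall inside even the Day 68 close, conception would have to precede Day 1 by 140 − 67 = 73 days. A pregnancy that old should be positive on the Visit 2 test, which leads to removal.

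Removal is not the main cause. Conception on Day 14 with a positive test on Day 28 closes the window at Day 58, 44 days after conception. A participant kept to Day 35 would still fall far outside it. The gap comes from the 30-day limit and the lack of outcome follow-up; earlier removal only widens it.

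**Expected number of pregnancies**, taking all 46 to the 35-day maximum, which overstates exposure:
- 46 × (35/30) × 0.002 = 0.11
- 46 × (35/30) × 0.01 = 0.54

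With a further assumed anomaly risk of 1 to 5% per pregnancy, the expected number of anomalies is 0.11 × 0.01 = 0.001 to 0.54 × 0.05 = 0.03 over the whole trial, placebo included.

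**The case against.** Four points count against making much of this.

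First, the pregnancy is not hidden. The rest of the Section 7.4 sentence takes it to the IRB, and to the monitoring committee, FDA and NCCIH wherever the enrollment log is reported. That stands: what is missing is the outcome.

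Second, a reader might infer that a birth defect could never be recorded, or would necessarily be absent from the safety reports. The documents do not support that. The 30-day limit governs routine recording by staff. The reporting duties in Section 7.4 carry no such limit, and several run from the investigator becoming aware. An anomaly made known later could still be reported, as could one diagnosed before birth and volunteered inside the window. Section 8 also leaves room for data collection after discontinuation. The supportable statement is that the outcome is not actively sought.

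Third, a reader might infer that the SAE list and the pregnancy rule contradict each other. They do not. The list classifies events that come to light; it does not promise follow-up until each criterion could occur. The passages that do sit badly together are removal from the study (Sections 6.2.2 and 7.4) and the open-ended data collection in Section 8.

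Fourth, this is a four-week biomarker study with contraception required and very few pregnancies expected. That limits the severity. It also makes the remedy nearly free.

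**Conclusion.** The point holds as a gap in safety ascertainment, of low severity. Under the stated rules no birth after study-drug exposure falls inside the SAE recording window, and nothing in the plan seeks the outcome. The smallest margin is 59 days (birth at 22 weeks' gestation) and the smallest margin to term is 185 days. Both rest on the assumed conception and gestation figures, but the conclusion would survive large changes in them.

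The conclusion is limited to births: an early pregnancy loss could occur inside the window. The expected counts, about 0.1 to 0.5 pregnancies and far fewer anomalies, rest on assumed rates. The consent forms are reviewed separately (Section 11.1) and were not available, so they may already address pregnancy follow-up. Nothing here affects the primary analysis of brain GSH.

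**What to change.** 1. Reconcile Section 7.3 (recording window), Sections 6.2.2 and 7.4 (removal) and Section 8 (data collection after discontinuation), so that the plan says one thing about data collection after a pregnancy. This concerns recording and reporting only; no clinical rule is proposed.
2. Record any pregnancy arising on study drug in the AE/SAE log as well as the enrollment log.
3. Exempt pregnancy outcome from the 30-day limit and the two-week follow-up limit, and seek the outcome by phone. An anomaly can then be recorded as the SAE that Section 7.3 says it is.

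The cost is a short protocol amendment, probably matching consent wording, and a few calls for probably no more than one participant. Contact with 16- and 17-year-olds needs some care, because Section 6.2.2 says parents are not told pregnancy results; the arrangement for reaching a minor has to respect that.
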